9.4.4 Selection of Doses in the Study

Selection of elenbecestat (E2609) 50 mg per day is based on the results (PD, safety, and tolerability) from the completed Phase 1 studies and interim data from the ongoing Phase 2 Study 202. Study 202 is currently evaluating the PD effects (reduction from baseline in CSF A β levels) of 5, 15, and 50 mg of elenbecestat (E2609) given daily. An interim PD analysis has been performed on the degree of CSF A β reduction achieved with elenbecestat (E2609) 5, 15, and 50 mg per day. Based on the PK/PD modeling results, elenbecestat (E2609) 50 mg per day reduced median CSF A β by approximately 70%. (revised per Amendment 03) Based on these data, elenbecestat (E2609) 50 mg per day dose was selected as a viable dose for this study. Subjects will be stratified according to region (7 levels), clinical dementia staging with no more than approximately 25% of the randomized subjects diagnosed with the early stages of mild dementia due to AD, and concurrent AD medication use. (revised per Amendments 01 and 02)

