9.7.1.6.1 PRIMARY EFFICACY ANALYSIS

The primary analysis will be based on an intent to treat philosophy without regard to adherence to treatment. The primary analysis of the change from baseline in CDR-SB at 24 months will be performed to compare elenbecestat (E2609) 50 mg per day versus placebo using a linear mixed effects model for repeated measures (MMRM) on the FAS. The MMRM model will include baseline CDR-SB as a covariate, with treatment group, visit, randomization stratification variables (ie, region [7 levels], clinical dementia [yes, no], and concurrent AD medication use at randomization (Visit 2) [yes, no]), and treatment group-by-visit interaction as fixed effects. (revised per Amendments 01 and 02) An unstructured covariance matrix will be employed to model the covariance of within subject effect; if MMRM fails to converge then a covariance structure with fewer parameters from the following list will be employed according to the prespecified order in the list until the MMRM converges. The list of covariance structure will include Heterogeneous Toeplitz, Toeplitz, Heterogeneous Compound Symmetry, and Compound Symmetry. This primary analysis will include all observed post baseline data of the change from baseline in CDR-SB without imputation of missing values. The treatment effect for elenbecestat (E2609) versus placebo will be compared at 24 months based on MMRM model. The LS means and difference in LS means between elenbecestat (E2609) treatment group and placebo, and corresponding 95% CI will be presented.

The null hypothesis is that there is no difference in the mean change from baseline in CDR-SB at 24 months between elenbecestat (E2609) 50 mg per day and placebo. The corresponding alternative hypothesis is that there is a difference in the mean change from baseline in CDR-SB at 24 months between elenbecestat (E2609) 50 mg per day and placebo.

The primary analysis will be repeated to minimize the impact of change in concomitant AD medications where efficacy data after initiation of new AD medications and increase of current AD medications will be censored.

The following sensitivity analysis will be conducted to evaluate the impact of missing data: the primary endpoint will be analyzed using ANCOVA after multiple imputation. The ANCOVA model will include baseline CDR-SB as a covariate, with treatment group and randomization stratification variables as factors.

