9.7.1.6.2 SECONDARY EFFICACY ANALYSES

The secondary analyses will be performed only if the primary analysis is significant. The treatment effect for elenbecestat (E2609) 50 mg/day versus placebo, for each secondary efficacy endpoint, will be tested using a sequential testing procedure at a significance level of 2-sided $\alpha = 0.05$, ie, any test will start only if the test with higher hierarchical order is significant. The final hierarchical order will be specified later in the statistical analysis plan before database lock.

Time to worsening of CDR scores by 24 months will be analyzed on the FAS using Cox regression model for treatment effect adjusting for randomization stratification factors. Time to worsening of a CDR score is defined as time from randomization to worsening of the CDR score (ie, the first worsening in 2 consecutive scheduled visits). For subjects whose CDR scores have not worsened by the end of study, the time to worsening of the CDR score will be censored at the date of last CDR assessment for these subjects.

Time to conversion to dementia for subjects who were not clinically staged as dementia at Baseline based on clinical diagnosis will be analyzed on the FAS using Cox regression model for treatment effect adjusting for randomization stratification factors. Proportion of subjects with dementia diagnosis at 24 months will be estimated using Kaplan—Meier method based on time to conversion to dementia based on clinical diagnosis. Time to conversion to dementia for subjects who were not clinically staged as dementia at Baseline based on clinical diagnosis is defined as time from randomization to conversion to dementia based on clinical diagnosis. For subjects without clinical dementia by the end of study, the time to conversion to dementia based on clinical diagnosis will be censored at the date of last dementia diagnosis.

The rate of change over time (mean slope) based on change from baseline in the CDR-SB will be analyzed using linear mixed effects (LME) models for multivariate normal data derived from a random coefficient model (slope analysis), where the mean slope in each group depends on a continuous assessment time. The LME model will include baseline CDR-SB, randomization stratification variables, assessment time, and treatment group-by-assessment time.

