The other continuous secondary efficacy endpoints as defined above will be analyzed using the same MMRM model as the primary efficacy analysis to compare elenbecestat (E2609) 50 mg per day versus placebo on the FAS, using baseline value corresponding to the response variable in the model.

The relationship between clinical changes at 24 months (CDR-SB, ADAS-cog₁₄, MMSE, and FAQ) and changes in each of the biomarkers (amyloid PET, CSF t-tau and p-tau, vMRI, and fMRI) at 24 months, will be evaluated using an ANCOVA model. (revised per Amendment 01) Changes in clinical scales at 24 months will be the response variables and either continuous or categorical change of biomarkers will be independent variables. The ANCOVA model will also include baseline value for clinical scale as a covariate,

randomization stratification variables, treatment group as factors, and other terms as appropriate.

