9.3.1 Inclusion Criteria

Subjects must meet all of the following criteria to be included in this study:

1. MCI due to AD or Mild AD according to the National Institute of Aging – Alzheimer’s Association (NIA-AA) core clinical criteria and must have all of the following:
 - a. MMSE score equal to or greater than 24
 - b. CDR global score of 0.5
 - c. CDR Memory Box score of 0.5 or greater
2. A history of subjective memory decline with gradual onset and slow progression over the last 1 year before Screening; this MUST be corroborated by a study partner
3. Cognitive impairment of at least 1 SD from age-adjusted norms in total recall or delayed recall on the ISLT.
4. Positive biomarker for brain amyloid pathology as indicated by at least 1 of the following:
 - a. PET assessment of amyloid imaging agent uptake into brain. Note: amyloid PET screens will be performed according to local regulatory guidelines and thus may be restricted for those subjects who are not suitable for LP to obtain CSF for testing of eligibility.
 - b. CSF assessment of A β (1-42)

NOTE: Subjects may undergo both the amyloid PET and CSF assessments, but need a positive amyloid result in only 1 of the 2 procedures to confirm eligibility. Subjects who consent to amyloid PET or CSF for eligibility purposes are not required to participate in the amyloid PET or CSF longitudinal substudies. Use of a historical amyloid PET (conducted within 12 months before the planned date of randomization) is acceptable for determination of eligibility but will not suffice for the baseline assessment if the subject wishes to consent to the amyloid PET longitudinal substudy. The historical imaging data must be made available to the sponsor.
5. Male or female subjects between 50 and 85 years of age, inclusive at the time of consent
6. If receiving an AChEI or memantine or both for AD, must be on a stable dose for at least 12 weeks prior to Randomization. Treatment-naïve subjects with AD can be entered into the study.

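### The two Cox models leave out baseline CDR-SB, which the primary and slope models use; adding it is an almost free improvement in power, not a correction of an invalid analysis.

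*Protocol*

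**What the plan says.** Section 9.7.1.6.2 gives both time-to-event secondary endpoints the same model, fitted on the FAS "using Cox regression model for treatment effect adjusting for randomization stratification factors". Section 9.7.1.6.1 lists those factors as "region [7 levels], clinical dementia [yes, no], and concurrent AD medication use at randomization (Visit 2) [yes, no".

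The other confirmatory models do adjust for the starting score. For the primary analysis, "The MMRM model will include baseline CDR-SB as a covariate", and the multiple-imputation ANCOVA in the same section does so too. For the slope analysis, "The LME model will include baseline CDR-SB, randomization stratification variables, assessment time, and treatment group-by-assessment time". The remaining continuous secondary endpoints are modelled "using baseline value corresponding to the response variable in the model".

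The conversion endpoint is restricted by definition: "Time to conversion to dementia for subjects who were not clinically staged as dementia at Baseline based on clinical diagnosis". Section 9.3.1 requires every subject to enter with a "CDR global score of 0.5", and Section 9.4.4 allows "no more than approximately 25% of the randomized subjects diagnosed with the early stages of mild dementia due to AD".

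**The concern.** Among the confirmatory efficacy endpoints, only these two are analysed without a baseline score. In the conversion analysis the clinical-dementia factor has one level, so only region and AD-medication use still vary, and neither measures severity. Global CDR cannot fill the gap, because everyone enters at 0.5. CDR-SB sums the same six domains and can still separate subjects within that level. It is plausible that a subject nearer the dementia threshold crosses it sooner.

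If so, leaving the covariate out of a Cox model costs power. Both endpoints are tested in the fixed sequence that follows a significant primary result, so lost power could matter beyond the endpoint itself.

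**Working it through.** **The plan's own figure.** The protocol gives no event rate, hazard ratio or power for the Cox endpoints. The only sample size it states is for the primary endpoint (Section 9.7.2), and that reproduces:

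- Difference: 0.25 × 1.75 = 0.4375; SD 2.05; two-sided alpha 0.05; power 90%.
- n per arm = 2(1.96 + 1.2816)² × 2.05² / 0.4375² ≈ 462 (463 by t-test).
- With 30% dropout: 462/0.7 = 660 and 463/0.7 = 662 per arm, against 665 stated. With 665 × 0.7 = 465.5 evaluable per arm, power is 90.2%.

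**Numbers in the Cox analyses.** CDR worsening uses up to 1330 subjects. Conversion uses at least about 1330 × 0.75 ≈ 998, because of the 25% cap.

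**Simulation.** There were 1500 trials per scenario, with 1:1 allocation, exponential event times, 24 months of follow-up and 30% exponential dropout. Each trial was fitted with treatment alone and with treatment plus one standardised covariate, which stands for what baseline CDR-SB adds beyond the stratification factors. From the documents come the sample sizes, the dropout, the allocation and the alpha. Assumed are the hazard ratio (0.75), the placebo event proportion by 24 months (30% or 40%) and the log hazard ratio per SD of the covariate (0 to 0.8, that is a hazard ratio per SD of 1 to about 2.2).

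Power in percent, without → with the covariate:

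| Log-HR per SD | Conversion, N = 998, 30% events | Conversion, N = 998, 40% events | CDR worsening, N = 1330, 30% events | CDR worsening, N = 1330, 40% events |
|---|---|---|---|---|
| 0 | 57.9 → 58.1 | 68.3 → 68.4 | 71.1 → 71.5 | 84.1 → 84.1 |
| 0.3 | 57.6 → 58.2 | 71.3 → 72.5 | 68.2 → 69.5 | 80.9 → 81.7 |
| 0.5 | 54.7 → 57.9 | 66.0 → 70.5 | 66.4 → 69.6 | 79.1 → 82.9 |
| 0.8 | 49.1 → 57.5 | 60.7 → 72.2 | 63.1 → 70.0 | 74.0 → 84.0 |

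The gains are therefore 0.0 to 0.4 points at 0, 0.6 to 1.3 at 0.3, 3.2 to 4.5 at 0.5 and 6.9 to 11.5 at 0.8. Monte Carlo error is about √(0.5 × 0.5/1500) = 1.3 points per power figure, and less for the paired differences.

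**Checks.**

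- The Schoenfeld formula, power = Φ(|ln HR|√d/2 − 1.96), gives 70% for d = 300 and 82% for d = 400 at HR 0.75. The non-prognostic runs with N = 1330 had about 302 and 407 events and power of 71% and 84%.
- With HR 0.80 and 40% events, the gains at 0.5 per SD were 5.4 points (conversion: 46.9 → 52.3) and 4.3 points (worsening: 60.1 → 64.4).
- A separate simulation of conversion rounded event times up to three-monthly visits (1000 subjects, 35% placebo conversion, HR 0.75, 600 runs). It gave 66.5% both ways with no prognostic value, then 60% v 63%, 56% v 65% and 52% v 62% at hazard ratios per SD of 1.5, 2.0 and 2.5.

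**The hazard ratio.** Without the covariate the average estimate moved from 0.75 to about 0.76 at 0.5 per SD and about 0.775 at 0.8 per SD.

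**The case against.** A Cox model adjusted for the randomization strata is conventional and valid. Nothing in Section 9.7.1.6.2 is contradicted elsewhere, and using baseline CDR-SB in models of CDR-SB change does not oblige the plan to use it for a clinical-diagnosis event. All of that stands, and it is why this is an improvement and not an error.

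The size also rests on assumptions. Entry is narrow (global CDR 0.5 and MMSE of 24 or more for everyone), and no section says how strongly CDR-SB predicts events within that range. The larger gains need a hazard ratio of about 2 or more per SD. This stands too.

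It could also be said that the analysis plan may add covariates. That carries less weight: the protocol states the covariate set for these models, and what it expressly defers is the testing order.

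A reader might infer more than the documents support:

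- That the planned estimate is biased towards 1. The shift is largely non-collapsibility: 0.75 is the ratio conditional on the covariate, while 0.76 to 0.775 is largely a ratio averaged over it. Both equal 1 under the null.
- That one failure blocks all other secondary tests. This depends on where the two endpoints are placed, and the order is not yet fixed.
- That the constant clinical-dementia term damages the conversion model. A one-level factor simply drops out and changes no result.

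**Conclusion.** The point holds as a free improvement on two secondary endpoints. Both Cox models omit a baseline score that the primary and slope models use, and the conversion model is left with no severity term. Type I error and the primary analysis are untouched.

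Under the assumed hazard ratio, event rates and dropout, the power recovered runs from about 0 to about 12 points, depending on a prognostic strength that the protocol does not give. Adjusting did not lower power in any simulated scenario. The case is strongest for conversion. For CDR worsening the dementia factor still varies and captures part of severity, so the gain there may be smaller than simulated.

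**What to change.** In Section 9.7.1.6.2, and wherever the synopsis repeats it, state before unblinding that both Cox models include baseline CDR-SB as a continuous covariate alongside the stratification factors, and that the reported hazard ratio is conditional on it. Removing the clinical-dementia term from the conversion model is editorial only. Section 9.7.1.6.3 analyses time to change of AD treatment in the same way as conversion, so say whether the covariate carries over.

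The cost is a sentence. CDR is rated at Visit 2 before the first dose, and the FAS already requires a baseline value of the primary measure, so no data are added and no subject is lost.

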9.7.1.6.3 EXPLORATORY EFFICACY ANALYSES

Time to change of concomitant AD treatment will be analyzed similarly to that for time to conversion to dementia based on clinical diagnosis. Time to change of concomitant AD treatment is defined as time from randomization to the first dose increase and/or initiation of treatment with AChEI or memantine after randomization. For subjects without any change of concomitant AD treatment by the end of study, the time to change of concomitant AD treatment will be censored at the date of last assessment of concomitant medication.

The proportion of subjects with any change of concomitant AD treatment at 24 months will be analyzed similarly to that for proportion of subjects with dementia diagnosis at 24 months.

The rate of change over time (mean slope) based on change from baseline in the NPI-10 item will be analyzed in a manner similar to that used for the rate of change over time (mean slope) based on change from baseline in the CDR-SB.

The analysis of the following exploratory efficacy endpoints will be performed to compare elenbecestat (E2609) versus placebo using the appropriate prespecified statistical methods including MMRM model, analysis of covariance model (ANCOVA), etc. For each exploratory efficacy endpoint, the treatment effect for elenbecestat (E2609) 50 mg per day versus placebo will be tested at a significance level of 2-sided $\alpha = 0.05$.

- Change from baseline in NPI-10 item at 24 months
- Change from baseline in EQ-5D (subject self-reported, study partner self-reported, and subject measured by proxy) and QOL-AD (subject and study partner) at 24 months
- Change from baseline in Zarit's Burden Interview at 24 months

Additional analyses may be performed as needed.

9.7.1.7 Pharmacokinetic, Pharmacodynamic, Pharmacogenomic, and Other Biomarker Analyses

9.7.1.7.1 PHARMACOKINETIC ANALYSES

Safety Analysis sets will be used for individual elenbecestat (E2609) plasma and CSF concentration listings. The PK Analysis Set will be used for the summaries of elenbecestat (E2609) plasma and CSF concentrations.

A population PK approach will be used to characterize the PK of elenbecestat (E2609). The effect of covariates (ie, demographics) on elenbecestat (E2609) PK will be evaluated. The PK model will be parameterized for clearance (CL) and volumes of distribution. Derived exposure parameters such as AUC will be calculated from the model using the individual posterior estimate of CL and dosing history.

9.7.1.7.2 PHARMACOKINETIC-PHARMACODYNAMIC

The PK/PD relationship between CSF biomarker levels and plasma PK parameters or CSF concentrations of elenbecestat (E2609) will be explored graphically and any emergent relationship will be explored through population PK/PD modeling. These PK parameters include maximum observed concentration (C_{max}), and $AUC_{(0-24)}$ derived from the population PK model. The PK/PD relationship between plasma PK parameters and CSF concentrations of elenbecestat (E2609) with other biomarkers may also be explored using similar methods.

Additionally, the relationship between various PK parameters (eg, C_{max}) or CSF concentrations of elenbecestat (E2609) and CDR-SB at 24 months, and the relationship between various PK exposure parameters or CSF concentrations of elenbecestat (E2609) and the change from Baseline for 24 months in ADAS-cog₁₄, and the MMSE, will be explored graphically. Any emergent relationships will be explored through population PK/PD modeling. The relationship between exposure to elenbecestat (E2609) and most frequent AEs will also be explored.

9.7.1.7.3 PHARMACODYNAMIC, PHARMACOGENOMIC, AND OTHER BIOMARKER ANALYSES

The analysis of the biomarker endpoints defined as below will be performed to compare elenbecestat (E2609) versus placebo using the appropriate prespecified statistical methods including MMRM model, analysis of covariance model (ANCOVA), etc. These analyses will be conducted without adjustment for multiplicity or sequential testing. For each endpoint, the treatment effect for elenbecestat (E2609) 50 mg per day versus placebo will be tested at a significance level of 2-sided alpha = 0.05.

- Change from baseline in amyloid PET SUVR composite at 24 months for brain amyloid levels
- Change from baseline in CSF biomarkers t-tau and p-tau at 24 months
- Change from baseline in CSF amyloid biomarkers $A\beta(1-40)$, $A\beta(1-42)$, and $A\beta(1-x)$ at 24 months
- Change from baseline in total hippocampal volume at 12 and 24 months using vMRI
- Change from baseline in the preservation of connectivity on fMRI from predefined anatomical regions connectivity maps (eg, precuneus, inferior frontal sulcus)

The relationship between exposure (in CSF, plasma) of elenbecestat (E2609) with potential biomarkers of Alzheimer's disease as deemed appropriate will be evaluated using appropriate statistical model with the continuous changes in biomarker at 24 months as response variables and exposure variables (in CSF, plasma) of elenbecestat (E2609) as independent variables.

9.7.1.8 Safety Analyses

Evaluations of safety will be performed on the Safety Analysis Set. The incidence of AEs, out-of-normal-range laboratory safety test variables, abnormal ECG findings, and out-of-range vital signs, suicidality, results of the sleep questionnaire, along with change from baseline in laboratory safety test variables, ECGs, and vital sign measurements will be summarized by treatment group. (revised per Amendment 01)

9.7.1.8.1 EXTENT OF EXPOSURE

The Duration of exposure to study drug will be summarized as cumulative extent of exposure in categories with 3-month increment. The cumulative number and percent of subjects in each applicable exposure category will be presented by treatment group. Duration of exposure will be summarized using descriptive statistics as well as by 3-month duration categories using counts. The number and percent of subjects within each duration category will be presented by treatment group. Overall exposure (number of subject-months) is defined as summation over all subjects' exposure durations and will be summarized by treatment group.

9.7.1.8.2 ADVERSE EVENTS

The AE verbatim descriptions (investigator terms from the eCRF) will be classified into standardized medical terminology using the Medical Dictionary for Regulatory Activities (MedDRA). AEs will be coded to the MedDRA (Version 19.0 or higher) lower level term closest to the verbatim term. The linked MedDRA PT and primary system organ class (SOC) are also captured in the database.

A TEAE is defined as:

- An AE that emerges during treatment within 4 weeks of the last dose of study drug, having been absent at pretreatment (Baseline) or
- Reemerges during treatment, having been present at pretreatment (Baseline) but stopped before treatment, or
- Worsens in severity during treatment relative to the pretreatment state, when the AE is continuous.

Only those AEs that are treatment-emergent will be included in summary tables. All AEs, treatment-emergent or otherwise, will be presented in subject data listings.

The TEAEs will be summarized by treatment group on the Safety Analysis Set. The incidence of TEAEs will be reported as the number (percentage) of subjects with TEAEs by SOC and PT. A subject will be counted only once within an SOC and PT, even if the subject experienced more than 1 TEAE within a specific SOC and PT. The number (percentage) of subjects with TEAEs will also be summarized by maximum severity (mild, moderate, or severe). The number (percentage) of subjects with TEAEs will also be summarized by relationship to study drug (Yes [related] and No [not related]).

The number (percentage) of subjects with treatment-related TEAEs will be summarized by SOC and PT. Treatment-related TEAEs include those events considered by the investigator to be related to study drug. The number (percentage) of subjects with treatment-related TEAEs will also be summarized by maximum severity (mild, moderate, or severe).

AEs will be summarized by the following subgroups: region, , prior treatment with AChEIs or memantine (no or yes), and clinical subpopulation (MCI due to AD or the early stages of AD). (revised per Amendment 01)

The number (percentage) of subjects with TEAEs leading to death will be summarized by MedDRA SOC and PT for each treatment group. A subject data listing of all AEs leading to death will be provided. The number (percentage) of subjects with treatment-emergent SAEs will be summarized by MedDRA SOC and PT for each treatment group. A subject data listing of all SAEs will be provided. The number (percentage) of subjects with TEAEs leading to discontinuation from study drug will be summarized by MedDRA SOC and PT for each treatment group. A subject data listing of all AEs leading to discontinuation from study drug will be provided.

